## 4. Research necessity and background

Post-COVID-19 conditions are a novel and poorly understood clinical disease with life-affecting ramifications, and recent studies have shown that patients have worsened their autonomic nervous system after COVID-19 and are potentially at risk of autonomic dysregulation/autonomic neuropathy.

Currently, most patients undergoing general anesthesia are using neuromuscular blockers, and the residual effect of neuromuscular block delays the recovery of autonomic functions of the body after surgery, and causes problems such as deterioration of bladder and bowel function after surgery. Therefore, reverse premise is used for postoperative muscle relaxation recovery, and clinically, sugammadex and neostigmine have been used a lot. Sugammadex generally provides rapid recovery, including recovery from muscle relaxation after surgery, compared to neostigmine, but postoperative outcomes have been reported with limited coverage in postoperative patients. Therefore, in this study, we

expect that sugammadex will help restore bowel function and lung function more than neostigmine after surgery in patients who have recovered from COVID-19 infection.

## 5. Risk/Benefit Analysis

Currently, most patients undergoing general anesthesia are using neuromuscular blockers, and reverse agents are used to restore muscle relaxation after surgery. Clinically sugammadex and neostigmine have been widely used (both of which are standard treatments). This study compares the results of the two drugs used in clinical trials and there is no additional risk from clinical trials, except for general side effects caused by general anesthesia. However, there is a risk of personal information exposure, and this will be minimized through encryption and access restrictions to protect personal information. There is no direct benefit to subjects from the trial, and the information from this study may be used to help with future clinical applications.

## 6. Research Objectives

To compare the effects of sugammadex on postoperative recovery in patients with COVID-19 infection and regular abdominal surgery within one year of treatment. In particular, we want to check the occurrence of dysuria after alcohol.

## 7. Number of target subjects and basis for calculation

In this study, based on the results of the previous paper reported by Han et al., the target number of subjects was calculated as follows (Jiwon Han, Ah-Young Oh, Yong-Tae Jeon, Bon-Wook Koo, Bo Young Kim, Donghyun Kim, Insung Hwang. Quality of Recovery after Laparoscopic Cholecystectomy Following Neuromuscular Blockade Reversal with Neostigmine or Sugammadex: A Prospective, Randomized, Controlled Trial. *J. Clin. Med.* 2021, 10, 938. <https://doi.org/10.3390/jcm10050938>).

The primary variable was based on the frequency of dysuria (6/38 vs 1/39) and the number of samples was checked using the G\*Power program. The allocation ratio for both patients was 1, significance 0.05, and power 0.9, set as a two-tailed test and expected the dropout rate to be more than 10%, and calculated the number of test subjects as 112 per group, a total of 224.

## 8. Selection/Exclusion Criteria

Inclusion criteria

American anesthesiology physical status I-III patients between the ages of 20 and 70 who are

scheduled to have regular abdominal surgery that is expected to take more than one hour and have been diagnosed positive for COVID-19 in the past year and have received oxygen therapy.

Regular surgery is a concept that contrasts with emergency surgery and refers to surgery in which sufficient pre-examination and treatment are performed before the start of surgery.

(ASA I: healthy patients, II: patients with mild illness but no impact on daily life, III: patients with illness that affects daily life)

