#### Exclusion criteria

1. Patients currently infected with COVID-19.
2. 1 Patients under 9 years of age or over 70 years of age
3. Patients who are planning to use a heart-lung machine during surgery (e.g., open-heart surgery, heart transplantation, lung transplantation, etc.)
4. Patients who are expected to undergo surgery within one hour or are scheduled to leave the hospital within 48 hours after surgery
5. Those who show active lesions on lung imaging images during preoperative screening or who are expected to be difficult to remove intubation immediately because endotracheal intubation maintenance is required for postoperative breathing management
6. Those who are hypersensitive to Benzodiazepines, propofol, remifentanyl, fentanyl citrate, rocuronium bromide, sugammadex, flumazenil, and other anesthetics
7. Those with myasthenia gravis or myasthenia gravis syndrome
8. Those with cognitive impairment who cannot understand the instructions and consent manual of this study
9. Other cases where the researcher determines that he or she is not suitable for participating in this study

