## **13. Study design and methods**

1. This study is conducted in patients scheduled for surgery under general anesthesia in a

single-organ, randomized, parallel design, and double-blinded.

Study subjects who have completed screening tests and voluntarily agreed to participate in this study among subjects who meet the inclusion/exclusion criteria will be randomized 1:1 to the Sugammadex injection group or the neostigmine injection group (control). The assignment of the two groups is randomized by computer-generated randomization method by a table using [www.randomization.com](http://www.randomization.com). The expected research flow chart is as follows.

2. After the patient enters the operating room, the patient is equipped with an electrocardiogram, oxygen saturation, esophageal thermometer, electroencephalography, non-invasive blood pressure monitoring device, and muscle relaxation monitoring equipment (TOF equipment). The method of anesthesia is according to the standard anesthesia method and is described in detail below.

3. Preanesthetic treatment: Midazolam 2 mg

4. Anesthesia inducer: Anterior venous anesthesia (propofol 2~1.5 mg/kg)

5. Neuromuscular blockers: Rocuronium 0.6 mg/kg IV in tracheal intubation , additional administration of rocuronium to keep TOF below 2 during surgery, 0.15 mg/kg.

6. Neuromuscular reversal: TOF results are checked at the end of surgery and neostigmine or sugammadex is administered according to the instructions. If TOF < 2, postpone administration until TOF 2 or higher spontaneously recovers. When recovering from TOF 2 or more, a prepared neuromuscular reversal agent is administered.

Neostigmine 50µg/kg + glycopyrrolate 0.01mg/kg in the Neostigmine group

Sugammadex 2mg/kg from Sugammadex group

Neuromuscular reversal is received and prepared in advance by a separate medical staff (a separate anesthesiologist who does not participate in the patient's anaesthesia) using the drug and the corresponding prescription order is made separately at the time of leaving the patient recovery room. Since it is diluted with saline and prepared in a total of 5 cc, the patient and the patient's anesthesiologist will not know the drug until they leave the recovery room (double-blinded).

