#### 15. Effectiveness evaluation items and methods

Study endpoints

Primary endpoints

Whether urinary retention occurs 1 hour after surgery

Secondary endpoints

Surgery time and anesthesia time

Recovery time after anesthesia

Intraoperative bleeding, vital signs

Whether and how to administer additional sugammadex

Bladder volume assessed at 1 hour postoperative (summing of autologous urination volumes)

Recovery score and pain score assessed at 1 hour after surgery

First fart time

Whether urinary retention occurs at 24 or 48 hours after surgery

Presence of acute lesions on chest x-ray 2 days after surgery

Actual use of pain and nausea control medications

Other intraoperative events (such as arousal (open eyes), involuntary movements, adverse events and unexpected side effects)

Independent variables

Patient gender, age, weight, height

American Academy of Anesthesiology Physical Classification (ASA class)

Heart rate, blood pressure, oxygen saturation (SpO2), muscle relaxation monitoring score (TOF)

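### Operation type is neither a stratification factor, a listed variable nor an analysis term, so the broad surgical mix adds avoidable variance to first flatus and bladder volume

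*Combined protocol and SAP*

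**What the plan says.** **Eligibility (Section 8).** The surgical criterion is that patients are "scheduled to have regular abdominal surgery that is expected to take more than one hour". Regular is explained only as the opposite of emergency. Exclusion criterion 4 removes patients expected to have operations shorter than an hour or "scheduled to leave the hospital within 48 hours after surgery", and criterion 5 removes those in whom immediate extubation is expected to be difficult. Use of a heart-lung machine is also excluded. Nothing limits the organ, the site within the abdomen, or open versus laparoscopic access.

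**Allocation (Section 13, item 1).** Patients are assigned 1:1, "randomized by computer-generated randomization method by a table". No stratification factor is named.

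**Variables (Section 15).** The independent variables are sex, age, weight, height, "American Academy of Anesthesiology Physical Classification (ASA class"), vital signs and the muscle relaxation score. Surgery time, anaesthesia time and intraoperative bleeding appear among the secondary endpoints. Operation type and approach do not appear.

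**Analysis (Section 16).** Continuous variables go to a t-test or Mann-Whitney test, and categorical variables to a chi-squared or Fisher test. No covariate or stratum is mentioned.

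**Planning rates (Section 7).** "The primary variable was based on the frequency of dysuria (6/38 vs 1/39"), taken from a single earlier trial titled "Quality of Recovery after Laparoscopic Cholecystectomy Following Neuromuscular Blockade Reversal with Neostigmine or Sugammadex".

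**The concern.** A gallbladder operation, a bowel resection and a pelvic operation can all qualify. Time to first flatus and bladder volume plausibly depend on where and how the abdomen was opened. Section 4 names bowel function as an expected benefit of sugammadex, and first flatus is the only bowel endpoint. If operation class explains part of its spread, an unadjusted comparison carries that spread in its standard error when it need not.

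There is also a reporting cost. With no operation field in the listed variables, the report could not show that the arms were balanced by operation, or describe the operations to which the result applies.

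**Working it through.** **1. The plan's own figure.** Inputs from Section 7: 6/38 = 15.8% and 1/39 = 2.6% (difference 13.2 points), 1:1 allocation, "significance 0.05, and power 0.9, set as a two-tailed test". Exact power of the two-sided Fisher test first reaches 90% at 101 per group (power 0.902; 0.899 at 100). Then 101 × 1.10 = 111.1, rounded up to 112. The stated 112 per group reproduces, so this point does not concern an arithmetic error in the sample size.

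**2. Binary primary endpoint.** Assumptions, not in the documents: 30% of patients have a higher-risk operation class, with 3 or 5 times the retention risk of the rest. Overall rates are held at 15.8% and 2.6%, with 101 evaluable per arm and 20,000 simulated trials.

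| Relative risk between classes | Power, unadjusted chi-squared | Power, Mantel-Haenszel by class |
|---|---|---|
| 3 | 0.942 | 0.946 |
| 5 | 0.943 | 0.952 |

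The type I error of the unadjusted test stays at about 0.05. At a given overall rate, mixing classes adds no variance to a yes/no outcome.

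**3. Chance imbalance in operation class.** With share q and simple allocation of 112 per arm, the SD of the between-arm difference in share is √(2q(1−q)/112).
- q = 0.2: SD = √(0.32/112) = 0.0535; chance of a gap above 10 points = 6%.
- q = 0.5: SD = √(0.50/112) = 0.0668; chance = 13%.

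**4. Time to first flatus.** Let d be the difference in class means and s the within-class SD. The share of variance due to class is q(1−q)d² / (s² + q(1−q)d²). All inputs are assumptions.
- d = 12 h, s = 20 h, q = 0.2: 23.04/(400 + 23.04) = 0.05.
- d = 12 h, s = 15 h, q = 0.5: 36/(225 + 36) = 0.14.
- d = 24 h, s = 20 h, q = 0.2: 92.16/(400 + 92.16) = 0.19.
- d = 24 h, s = 15 h, q = 0.5: 144/(225 + 144) = 0.39.

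The standard error of the difference in means is SD × √(2/112). At the low end it falls from 20.57 × 0.1336 = 2.75 h to 20 × 0.1336 = 2.67 h once class is accounted for. At the high end it falls from 19.21 × 0.1336 = 2.57 h to 15 × 0.1336 = 2.00 h.

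**5. Any continuous endpoint, including bladder volume.** If class means differ by k within-class SDs, the variance is multiplied by 1 + q(1−q)k². This is 1.05 for q = 0.3, k = 0.5; 1.21 for q = 0.3, k = 1; and 1.25 for q = 0.5, k = 1. The required sample size rises by about 5% to 25%.

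**6. Size of a chance shift.** A 10-point imbalance with d = 24 h moves the flatus difference by 0.10 × 24 = 2.4 h. With d = 24 h, the total SD runs from √(225 + 92.16) = 17.8 h to √(400 + 144) = 23.3 h, so the unadjusted standard error is about 2.4 to 3.1 h. The shift is 0.8 to 1.0 standard error.

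**The case against.** Much of the opposing case stands.

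- **Bias.** A reader might infer that a chance excess of bowel or pelvic operations in one arm biases the comparison. It does not. Imbalance under randomisation is chance error, and the unadjusted standard error already includes it (step 6). The imbalance and the extra variance are one phenomenon, not two harms.
- **Primary endpoint.** A reader might infer that the retention comparison is undermined. Step 2 shows almost no effect.
- **Not recorded.** A reader might conclude that the operation will not be captured at all. The documents show only that it is not listed in Section 15. No case report form is included, a figure is missing, and checking eligibility requires knowing the scheduled operation. Surgery time and bleeding are partial proxies, but neither identifies the site or the approach.
- **Beyond repair.** Strata cannot be added to allocations already made. With 224 patients, however, adjustment for a recorded operation class recovers most of the precision.
- **Breadth.** The objective in Section 6 is abdominal surgery generally, so wide eligibility is a legitimate choice. The exclusions also narrow it, so not every elective abdominal operation over an hour qualifies. Section 13 calls the design single-organ, but no organ is named anywhere. I read this as single-institution, not as a surgical restriction.
- **Planning rates.** A reader might infer that the sample size is wrong because its rates come from one operation. The documents give no retention rate for the mixed population, so they cannot show that. Whether the rates transfer is a separate question, and stratification would not answer it.

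What survives is that the plan omits a plausible prognostic factor, known before surgery, from allocation, data and analysis, although including it costs little.

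**Conclusion.** The point holds as a cheap improvement of minor severity. The planned tests are valid and the primary endpoint is essentially unaffected (about 0.5 to 1 point of simulated power). For first flatus, operation class would account for roughly 5% to 39% of the variance, and bladder volume is exposed in the same way. The range rests on assumed class differences of 12 to 24 hours, within-class SDs of 15 to 20 hours and shares of 20% to 50%. None of these is in the documents, and if operation classes differ little the gain is small. The inability to show balance by operation from the listed variables does not depend on those assumptions, but it does depend on the operation not being captured elsewhere.

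**What to change.** 1. **Section 15:** add scheduled operation class and approach (open or laparoscopic) to the listed variables.
2. **Section 13, item 1:** for patients not yet randomised, use separate permuted-block lists for bowel or pelvic operations and for other abdominal operations. Surgery is elective, so the class is known at consent.
3. **Section 16:** compare first flatus with a rank test stratified by operation class, and bladder volume with a model adjusted for class. Report retention stratified by the same classes, with an exact stratified test if events are sparse. At 1/39, about 112/39 = 2.9 events are expected in the sugammadex arm, so sparse strata are likely.
4. **If stratified allocation is not adopted:** keep steps 1 and 3. Prespecified adjustment for the recorded class recovers most of the gain.

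Cost: two chart fields, slightly more handling for the person who opens allocations, and slightly more analysis work. The sample size need not change on this account.

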#### Exclusion criteria

1. Patients currently infected with COVID-19.
2. 1 Patients under 9 years of age or over 70 years of age
3. Patients who are planning to use a heart-lung machine during surgery (e.g., open-heart surgery, heart transplantation, lung transplantation, etc.)
4. Patients who are expected to undergo surgery within one hour or are scheduled to leave the hospital within 48 hours after surgery
5. Those who show active lesions on lung imaging images during preoperative screening or who are expected to be difficult to remove intubation immediately because endotracheal intubation maintenance is required for postoperative breathing management
6. Those who are hypersensitive to Benzodiazepines, propofol, remifentanyl, fentanyl citrate, rocuronium bromide, sugammadex, flumazenil, and other anesthetics
7. Those with myasthenia gravis or myasthenia gravis syndrome
8. Those with cognitive impairment who cannot understand the instructions and consent manual of this study
9. Other cases where the researcher determines that he or she is not suitable for participating in this study

#### Suspension and Elimination Criteria

If the surgical plan is changed and is not performed, the study will be discontinued and dropped.

### **9. Investigational Drug Information and Management**

Trial drug: Sugammadex is used for the reversal of neuromuscular blockade induced by rocuronium or vecuronium in patients 2 years of age and older, and is a colorless transparent vial containing a colorless to light yellow transparent solution, and the storage method of the drug is as follows. 1) Store at 2~30°C. Do not freeze. 2) Store in its original packaging to maintain shading. Vials removed from the packaging can be stored outside for up to 5 days.

Treaty: Korean neostigmine methyl sulfate injection (neostigmine) is used for the purpose of antagonizing the action of non-depolarizing muscle relaxants and is stored in room temperature shading in yellow vials containing a colorless transparent solution.

Management in this study: The drug is routinely applied in actual clinical practice and is stored and administered in accordance with the department policy of the Department of Anesthesiology and Pain Medicine along with other anesthetic drugs.

## **10. Recruitment method and consent procedure**

### 10.1 How to recruit candidates

- Recruitment is performed for patients who are scheduled to undergo general anesthesia for surgery. After explaining the contents of the study and the criteria for participation, the researcher receives the subject's consent form only for those who voluntarily wish to participate in the study. After that, the eligibility for participation in the study is determined and this study is carried out on those who are judged eligible through the selection/exclusion criteria.

### 10.2. How to obtain a consent form

- The principal investigator and the person in charge of the study shall verbally fully explain the contents and risks of the experiment to those who are willing to participate voluntarily before the clinical trial, and obtain written consent.
- The researcher may express his or her intention to drop out at any time and announce that there is no penalty.
- After sufficient explanation and confirmation of the subject's understanding, obtain a consent form to participate in the experiment.

## **11. When recruiting vulnerable targets, protection measures**

Do not recruit vulnerable targets.

## **12. Screening test items and methods**

[figure not shown]
This study does not perform additional screening tests other than general anaesthesia and general screening for surgical preparation (including basic blood, urine tests and chest X-rays).

## **13. Study design and methods**

1. This study is conducted in patients scheduled for surgery under general anesthesia in a

single-organ, randomized, parallel design, and double-blinded.

Study subjects who have completed screening tests and voluntarily agreed to participate in this study among subjects who meet the inclusion/exclusion criteria will be randomized 1:1 to the Sugammadex injection group or the neostigmine injection group (control). The assignment of the two groups is randomized by computer-generated randomization method by a table using [www.randomization.com](http://www.randomization.com). The expected research flow chart is as follows.

2. After the patient enters the operating room, the patient is equipped with an electrocardiogram, oxygen saturation, esophageal thermometer, electroencephalography, non-invasive blood pressure monitoring device, and muscle relaxation monitoring equipment (TOF equipment). The method of anesthesia is according to the standard anesthesia method and is described in detail below.

3. Preanesthetic treatment: Midazolam 2 mg

4. Anesthesia inducer: Anterior venous anesthesia (propofol 2~1.5 mg/kg)

5. Neuromuscular blockers: Rocuronium 0.6 mg/kg IV in tracheal intubation , additional administration of rocuronium to keep TOF below 2 during surgery, 0.15 mg/kg.

6. Neuromuscular reversal: TOF results are checked at the end of surgery and neostigmine or sugammadex is administered according to the instructions. If TOF < 2, postpone administration until TOF 2 or higher spontaneously recovers. When recovering from TOF 2 or more, a prepared neuromuscular reversal agent is administered.

Neostigmine 50µg/kg + glycopyrrolate 0.01mg/kg in the Neostigmine group

Sugammadex 2mg/kg from Sugammadex group

Neuromuscular reversal is received and prepared in advance by a separate medical staff (a separate anesthesiologist who does not participate in the patient's anaesthesia) using the drug and the corresponding prescription order is made separately at the time of leaving the patient recovery room. Since it is diluted with saline and prepared in a total of 5 cc, the patient and the patient's anesthesiologist will not know the drug until they leave the recovery room (double-blinded).

After checking the TOF ratio  $\geq 0.9$ , the endotracheal tube is removed. If muscle relaxation recovery is delayed for more than 0 minutes, more than 2 mg / kg of sugammadex can be used regardless of the group, in which case the administration and dosage should be recorded separately.

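### Making the reversal syringe up to 5 cc does not show that the two arms look alike, and the control regimen may not fit in that volume

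*Combined protocol and SAP*

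**What the plan says.** Section 13, item 6 describes three blinding measures.

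- The syringe is prepared by "a separate anesthesiologist who does not participate in the patient's anaesthesia".
- The paper trail is delayed: "the corresponding prescription order is made separately at the time of leaving the patient recovery room".
- The contents are brought to a fixed volume: "Since it is diluted with saline and prepared in a total of 5 cc". The protocol concludes from this that "the patient and the patient's anesthesiologist will not know the drug until they leave the recovery room".

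Section 9 describes the products. Sugammadex "is a colorless transparent vial containing a colorless to light yellow transparent solution"; neostigmine comes in "yellow vials containing a colorless transparent solution". The appearance of glycopyrrolate, which is part of the control regimen, is not given. Neither section states the strength of any product, and no opaque syringe, cover, coded label or check of matching appearance is described.

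Item 6 also ties extubation to a TOF ratio of at least 0.9 and says that additional sugammadex "can be used regardless of the group" when recovery is delayed. It does not name who decides. Item 9 gives the bladder scan to a separate doctor not involved in the intraoperative anesthesia, with retention defined as more than 600 ml.

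**The concern.** The separate preparer and the late order hide the allocation from the records. They do nothing about the object that the anesthesiologist holds. For that, the protocol relies on equal volume, and equal volume is not equal appearance. A tint that only one product may have, or a control syringe that cannot be kept to 5 cc, would each give the arm away.

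Section 22(2) runs the double-blind period up to exit from the recovery room. That window contains extubation, any additional sugammadex, the 1-hour bladder scan (primary endpoint) and the 1-hour recovery and pain scores (secondary endpoints). If additional sugammadex were given more readily in one arm because the arm was known, the treatment contrast itself would change. The recovery and pain scores are also open to influence if whoever elicits them knows the arm.

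**Working it through.** **Appearance.** Of the three measures, only dilution acts on what can be seen. Section 9 gives sugammadex a range from colorless to light yellow and neostigmine a single value, colorless. The ranges overlap at colorless; only sugammadex can depart from it. The yellow in the neostigmine description belongs to the vial, not the solution. So a tint may remain in one arm only, weakened by dilution to an extent that the documents do not state.

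**Volume.** The plan's figure of 5 cc cannot be reproduced, because the documents give no concentrations and no weight limits.

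Inputs from section 13, item 6: neostigmine 50 µg/kg (0.05 mg/kg), glycopyrrolate 0.01 mg/kg, sugammadex 2 mg/kg, total 5 mL.

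Assumed inputs: neostigmine 0.5, 1.0 or 2.5 mg/mL; glycopyrrolate 0.2, 0.4 or 1.0 mg/mL; sugammadex 100 mg/mL; body weight 70 kg as an example.

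Undiluted control volume at weight W = 0.05·W / c_neo + 0.01·W / c_gly.

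At 70 kg the control doses are 0.05 × 70 = 3.5 mg and 0.01 × 70 = 0.7 mg. With glycopyrrolate at 0.2 mg/mL:

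- neostigmine 0.5 mg/mL: 3.5/0.5 + 0.7/0.2 = 7.0 + 3.5 = 10.5 mL
- neostigmine 1.0 mg/mL: 3.5 + 3.5 = 7.0 mL
- neostigmine 2.5 mg/mL: 1.4 + 3.5 = 4.9 mL

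Heaviest patient whose control regimen fits in 5 mL = 5 / (0.05/c_neo + 0.01/c_gly). For example, 5 / (0.10 + 0.05) = 33.3 kg.

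| Glycopyrrolate (assumed) | Neostigmine 0.5 mg/mL | 1.0 mg/mL | 2.5 mg/mL |
|---|---|---|---|
| 0.2 mg/mL | 33 kg | 50 kg | 71 kg |
| 0.4 mg/mL | 40 kg | 67 kg | 111 kg |
| 1.0 mg/mL | 45 kg | 83 kg | 167 kg |

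Sugammadex at 70 kg: 2 × 70 = 140 mg, and 140/100 = 1.4 mL. It fits up to 5 / (2/100) = 250 kg. If either arm departs from 5 cc, it is therefore the control arm.

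**Outcome assessment.** The preparer takes no part in the patient's anesthesia; the scanning doctor took no part in the intraoperative anesthesia. Both descriptions could fit one person, and the scanning doctor is nowhere said to be blinded. The scan also leaves some room for judgement. The shape coefficients in item 9 run from 0.52 to 0.89, so a width × depth × length product between 600/0.89 = 674 and 600/0.52 = 1154 falls on either side of 600 ml depending on the coefficient chosen.

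**The case against.** The case for the plan as it stands has real weight.

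- A reader might infer that the blind rests on volume alone. It does not: the separate preparer and the delayed order are genuine safeguards.
- A reader might infer that section 9 states a definite colour difference. It does not: both solutions may be colorless, and dilution weakens any tint.
- A reader might take 71 kg as a general ceiling. It applies only with neostigmine at 2.5 mg/mL and glycopyrrolate at 0.2 mg/mL. Other assumed strengths move the limit as high as 167 kg, and the documents give no weight distribution.
- The primary endpoint is an ultrasound volume against a fixed threshold, taken by a doctor outside the intraoperative team. Extubation follows a measured TOF ratio, and additional sugammadex must be recorded. That the patient's anesthesiologist decides these steps is a reasonable inference, but the text names nobody.
- Section 4 says "Sugammadex generally provides rapid recovery, including recovery from muscle relaxation after surgery, compared to neostigmine". That cue comes from the drugs being compared and reaches anyone watching the TOF monitor; no syringe measure removes it.

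All of this stands, and it limits the finding. It does not supply what is missing: evidence that the syringes look the same, that 5 cc is achievable in the control arm, and that the bladder assessor is blinded.

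**Conclusion.** The point holds as a gap in the masking method. The protocol does not show that the two syringes are indistinguishable, and the anesthesiologist may be able to identify the arm before extubation and any additional sugammadex. The tint possibility comes from section 9 itself; whether it is visible after dilution is unknown. The overflow is conditional on stock strengths and weights that the documents omit: it arises at ordinary adult weights under several of the nine assumed combinations, not all.

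The likely effect on the primary endpoint is limited by the separate assessor and the 600 ml threshold, with the reservation that this assessor's blinding and distinctness from the preparer are not stated. The documents do not support the stronger conclusions that the anesthesiologist can identify the arm or that the trial is not double-blind. This is a cheap improvement worth making, and it has no bearing on the sample size.

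**What to change.** In section 13, item 6:

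- issue both arms in opaque or fully covered syringes labelled only with the study number;
- replace the 5 cc total with one common volume, confirmed from the stock strengths in use to hold the undiluted control regimen for the heaviest patient, and state those strengths.

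In section 13, item 9, state that the doctor who does the 1-hour bladder scan is blinded to arm and is not the preparer. Only on that condition should the same doctor record the 1-hour pain and recovery scores; otherwise those scores could pass to someone who knows the arm.

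Assigned doses do not change. The cost is syringe covers, a preparation sheet, a short protocol edit and a somewhat larger injection volume. The recovery-speed cue on the TOF monitor remains, which is a further reason to keep the 1-hour assessment with someone blinded to arm.

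### As printed, the trigger for additional sugammadex is a delay of more than zero minutes, which cannot separate rescue from routine use in either arm

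*Combined protocol and SAP*

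**What the plan says.** Section 13 sets out the sequence in items 5 and 6. During surgery the block is maintained, with "additional administration of rocuronium to keep TOF below 2 during surgery". At the end of surgery TOF is checked: "If TOF < 2, postpone administration until TOF 2 or higher spontaneously recovers". The prepared agent is then given. This is neostigmine with glycopyrrolate in the control arm; for the test arm the text reads "Sugammadex 2mg/kg from Sugammadex group". The tube is removed once the TOF ratio is at least 0.9.

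The rescue sentence comes next: "If muscle relaxation recovery is delayed for more than 0 minutes, more than 2 mg / kg of sugammadex can be used regardless". It goes on to say that this holds whichever group the patient is in, "in which case the administration and dosage should be recorded separately". No starting event for the delay is named, and no other section gives a delay time.

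Section 15 makes urinary retention at 1 hour the primary endpoint. It lists "Whether and how to administer additional sugammadex" among the secondary endpoints.

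**The concern.** A rescue rule needs a threshold that some patients meet and others do not. A delay of more than zero minutes is met by any positive delay, so as printed the rule does not limit who may receive sugammadex.

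Three things depend on it. First, it operates in both arms before the 1-hour primary endpoint, so control patients can receive the test drug before the outcome is measured. Section 4 describes recovery with sugammadex as generally faster than with neostigmine, so a delay rule would be expected to apply mainly to controls. Second, the frequency of additional sugammadex is itself a listed endpoint, and it has no fixed meaning if its trigger has none. Third, with no usable figure, two anaesthesiologists can apply different working thresholds, and rescue then reflects who was on duty as well as how the patient recovered.

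**Working it through.** **Reading the text.** The threshold itself involves no arithmetic, so the relevant places are set side by side.

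1. Section 13, item 6, rescue sentence: delay greater than 0 minutes, either arm, dose worded only as above 2 mg/kg, no starting event.
2. Same item, preceding sentence: TOF ratio of at least 0.9 before extubation. This suggests the recovery being awaited but gives no time limit.
3. Same item, earlier: the assigned agent waits for TOF 2 or higher. This is a condition on TOF, not a time.
4. Sections 15, 16, 17 and 22: no delay time.

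No other place supplies the missing figure.

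**Is the zero a damaged number?** Section 8 sets a lower age limit of 20. The matching exclusion item prints a stray 1 and then "Patients under 9 years of age or over 70 years of age", so a two-digit number was split there. In that case the digit was displaced and can still be seen; here none is visible. The parallel is suggestive, not proof.

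**The plan's own sample size.** Inputs from Section 7: 6/38 = 0.1579 and 1/39 = 0.0256, two-sided 0.05, power 0.9, 1:1 allocation, dropout taken as 10%.

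- Pooled formula, mean rate 0.0918: n = [1.960·√(2·0.0918·0.9082) + 1.282·√(0.1579·0.8421 + 0.0256·0.9744)]² / 0.1323² = (0.800 + 0.509)² / 0.01749 ≈ 98.05, so 99 per group. 99/0.9 = 110.
- Fisher's exact test: power is 0.899 at 100 and 0.902 at 101 per group. 101 × 1.1 = 111.1, so 112; 101/0.9 = 112.2, so 113.

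The stated 112 per group is reproduced.

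**Illustration of dilution.** The documents give no rescue rate, so r (share of controls rescued) and f (share of the between-arm difference lost in a rescued control) are assumptions. Evaluable n = 112 × 0.9 = 100.8, taken as 101 per arm. Diluted control rate = 0.1579 − r·f·0.1323. Power is by exact enumeration, two-sided 0.05.

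| r·f | Control rate | Power, uncorrected chi-squared |
|---|---|---|
| 0 | 0.1579 | 0.941 |
| 0.10 | 0.1447 | 0.902 |
| 0.20 | 0.1314 | 0.843 |
| 0.30 | 0.1182 | 0.760 |

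- Chi-squared power is 0.90 at r·f = 0.1034. That is r = 10.3% if f = 1, or 0.1034/0.5 = 20.7% if f = 0.5.
- Chi-squared power is 0.80 at r·f = 0.2551. That is r = 25.5% if f = 1, or 51.0% if f = 0.5.
- Fisher's test, which Section 16 gives as the alternative, starts at 0.902, reaches 0.90 at r·f = 0.0045 and 0.80 at 0.1637.
- The smallest expected cell is 101 × (0.1579 + 0.0256)/2 = 9.27 with no rescue, and 101 × (0.1182 + 0.0256)/2 = 7.26 at r·f = 0.30. The chi-squared test is therefore the relevant one over this range.

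**The case against.** The strongest objection is that the zero is probably not what the approved protocol says. The English text is rough, at least one other number in it is split, and damage of that kind is not a flaw in the plan. This stands as a limit: if the source shows a legible non-zero time, the threshold point falls away. It does not remove the need to check, because this is an operative figure that staff must apply and it cannot be recovered from elsewhere in the document.

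A reader might infer more: that Section 13 contradicts itself, because a delay counted from the end of surgery would include the wait for TOF 2 and open sugammadex before the assigned agent is given. The documents do not support that. Item 6 gives an order (wait, then give the assigned agent), the rescue sentence follows that step, and Section 15 calls the drug additional. The natural reading is a dose after the assigned agent. The starting event is unwritten, but that is a minor gap.

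A reader might also take the dose wording as a conflict with the assigned 2 mg/kg. It is only unclear: the text does not say whether it means a further dose, a total or a minimum. Section 7 is similarly loose, describing dropout as more than 10% although 112 is reproduced with 10%.

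Finally, some of the consequences are already contained. Use and dose are recorded and reported. The patient's anaesthesiologist is blinded until recovery-room exit, so uneven use of the rule would not follow from knowing the arm. Rescue is permitted and is not among the withdrawal criteria in Section 17, so analysis in the randomised arm is already the natural reading. These facts reduce the harm but do not supply a threshold.

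**Conclusion.** The point holds for the text as printed. A delay of more than zero minutes is not a usable rescue threshold, no other section supplies one, and the rule acts in both arms before the primary endpoint while also defining a secondary endpoint. It should be corrected. It is not established that the approved protocol contains the same figure.

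No effect on power is established. The dilution figures rest on assumed values of r and f, and use of rescue is permissive. The case f = 1 is the extreme: on the natural sequence a rescued control has already had neostigmine and glycopyrrolate. A reader might infer from the table that the trial is underpowered, but the figures do not show this, and Section 7 stands.

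**What to change.** Check the delay threshold in Section 13, item 6 against the approved source protocol, correct the sentence, and reconcile it with the sequence and assigned regimens earlier in that item. Which time or dose is right is for the investigators and the approved source; none is suggested here.

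Two minor clarifications can go into the same sentence: the event from which delay is counted, and what the wording above 2 mg/kg refers to. Optionally, Section 16 can state that patients given additional sugammadex are analysed in the arm to which they were randomised.

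The cost is a source check, one corrected sentence and one optional sentence. No new data are needed, since use and dose are already recorded, and the sample size does not change.
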